## 9.4 DATA SOURCES

Physicians will be identified according to their specialty as specified in the IMS OneKey lists. They will be sent an email to present them the survey and invite them to participate.

The survey is a primary data collection conducted through a web questionnaire.

The questionnaire will be developed and tested among 6 physicians for its comprehensibility, consistency and the appropriateness of medical terms. Physicians' comments will be implemented in the final version.

The translated versions of the questionnaire from English into local language will be done using the back and forth method (from English into local language and then from local language into English) to ensure an accurate translation.

The web questionnaire completion is estimated to take 10 to 15 minutes for the core questionnaires and around 5 minutes per prescription details reported.

## 9.5 STUDY SIZE

### 9.5.1 Sampling plan

The statistical unit considered is the physician who prescribes systemic thiocolchicoside. For each selected country, the sample survey will include physicians identified and recruited from one source: IMS OneKey reference lists of required specialists.

These lists may not cover all of the physicians who received the DHPC and EM or may include physicians who were not targeted for the DHPC and EM. Consequently a screening question will check whether the physician has prescribed systemic thiocolchicoside within the last 12 months and therefore can be considered as a prescriber. These lists will be restricted to the targeted specialists' population, i.e. selected specialists who are currently active and not retired in 2016 at the time of the survey.

As per sample size defined below and the number of selected countries and specialties, physicians will be stratified only per country and specialty (Table 9.5.1–1). Other criteria such

as region, age and gender of the prescriber are less relevant than country and specialty, since they may not be available in all countries or not be a determinant as important as country or specialty. The use of more strata would have needed a larger sample size.

A random stratified sampling method will be applied. As a first step, all lists will be merged, and then the eligible physicians will be divided into homogeneous groups, called strata, which are mutually exclusive (a physician can only belong to one stratum). This stratification will be based on the following criteria:

- Country: 4 possibilities,
- Specialty: 3 possibilities.

Thus,  $4 \times 3 = 12$  strata will be formed.

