#### **4.10 Milestones**

- Start of data collection: September 2016
- End of data collection: November 2016
- Submission of study report to EMA: June 2017

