**6. MILESTONES**

Milestone	Planned date
Registration in the EU PAS register	November 2015
Start of data collection	September 2016
End of data collection	November 2016
Final report of study results	June 2017

The table below summarises per country the time schedule of distribution of DHPC and EM.

	France	Greece	Italy	Portugal
Distribution of DHPC	April 2014	February 2014	February 2014	February 2014
Distribution of EM	26 April 2016	2 August 2016	October 2015	September 2015

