### 1) Physicians demographics and practice information:

Physician's related data include:

- Demographics (age, gender)
- Duration of practice
- Specialty
- Type of setting

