### 5) Awareness of and attitude towards the latest prescribing conditions and safety information:

- Awareness of the prescribing conditions and safety information about systemic thiocolchicoside presented in the DHPC and EM:

- Awareness of the prescribing conditions and safety information: main concerns perceived
- Sources of knowledge
- Reception of the DHPC by the physician and awareness about the EM
- Physician's intention to consider the prescribing conditions and safety warnings

6) Recent prescriptions details:

The following information related to up to the last five prescriptions to patients will be collected upon physician's recall memory:

- Approximate date of prescription of systemic thiocolchicoside
- Approximate patient' age at the time of prescription (age ranges: <16 or ≥16 years old)
- Gender
- Status at the visit for females of childbearing potential (using or not an effective method of contraception, pregnant or not, planning to be pregnant, breastfeeding)
- Indication for which the drug was prescribed
- Form, number of administrations and dose per administration per day
- Duration of use prescribed
- Concomitant treatment(s) ongoing or written at the time of prescription
- Main reasons for choosing systemic thiocolchicoside
- Information and recommendations provided to the patient when prescribing systemic thiocolchicoside containing medicinal products.

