#### Study objective:

The proportion of targeted physicians who received, understood and agreed to implement the latest prescribing conditions and safety information about systemic thiocolchicoside provided in the DHPC and EM will be evaluated. Analysis will be done in total and separately by specialty (GPs, rheumatologists and orthopaedists / orthopaedic surgeons) using proportions and the corresponding 95% Wald confidence intervals.

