#### **9.9.5 Generalisation of the survey results to the overall target population with adjustment**

Since the study design presents an over-sampling mainly in Greece or Portugal, and less frequent specialties as rheumatologists or orthopedists/ orthopedic surgeons and an under-sampling in France, Italy and of GPs, the raw survey results will not be generalised to the overall target population, except if a sample adjustment is applied. For more accuracy and transparency, both unweighted (i.e. raw data) and weighted results will be presented in the report.

Since the IMS lists may identify a limited number of physicians who were not targeted with the DHPC and EM, the results may be impacted.

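### The 2016 frame counts physicians who began practice after the 2014 DHPC mailing as targeted, and the prescribing screen cannot identify them, so measured DHPC receipt is diluted

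*Protocol*

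**What the plan says.** - **Frame.** Section 9.5.1 restricts the OneKey lists to the targeted specialists' population and explains that as "selected specialists who are currently active and not retired in 2016 at the time of the survey". It sets no condition on having been in practice in 2014.
- **Dates.** Section 6 states: "The table below summarises per country the time schedule of distribution of DHPC and EM". The DHPC dates are February 2014 for Greece, Italy and Portugal, and April 2014 for France. The EM followed in September 2015 (Portugal), October 2015 (Italy), April 2016 (France) and August 2016 (Greece). Section 4.10 gives "Start of data collection: September 2016", with collection ending in November 2016.
- **Objective.** Section 9.7.1 will evaluate "The proportion of targeted physicians who received, understood and agreed to implement the latest prescribing conditions and safety information".
- **Items collected.** Section 9.3 lists "Duration of practice" among the physician data and "Reception of the DHPC by the physician and awareness about the EM" under awareness.
- **Mismatch acknowledged.** Section 9.5.1 says the lists "may include physicians who were not targeted for the DHPC and EM" and, as a consequence, adds a screening question on prescribing within the last 12 months. Section 9.9.5 repeats that the lists "may identify a limited number of physicians who were not targeted with the DHPC and EM" and that results may be affected. It gives no handling.
- **A statement that does not fit.** Section 9.7.1 rules out a before-after or case-control design on the ground that the DHPC and EM had already gone to every physician of the selected specialties.

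**The concern.** A physician who entered practice after the mailing and prescribed thiocolchicoside in the past year passes every check in the plan. That physician sits in the denominator as targeted and will usually report not having received the letter. The screen that section 9.5.1 offers as its answer to list mismatch tests for recent prescribing, whereas the mismatch here concerns presence in practice in 2014.

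The effect runs in one direction: such physicians lower measured DHPC receipt. If that figure is read as how well the letter reached the physicians to whom it could have been sent, the letter looks less effective than it was. A larger sample would not remove this.

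**Working it through.** **Step 1. The plan's own figure.** Section 9.5.2 uses n = P(1 − P)z²/e². With P = 0.50, z = 1.96 and e = 0.04, n = 0.25 × 1.96² / 0.04² = 600.2, which agrees with the stated 600. The unweighted half-width at n = 600 is therefore 4.0 points.

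**Step 2. Gap between mailing and survey (sections 4.10 and 6).**
- France: April 2014 to September–November 2016 = 29 to 31 months.
- Greece, Italy, Portugal: February 2014 to September–November 2016 = 31 to 33 months.

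**Step 3. Share of later entrants.** The documents give no entry rate. Assume r = 1% to 5% per year and f = r × months / 12.

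**Step 4. Dilution.** If receipt among physicians in practice at the mailing is p, and no later entrant reports receipt, measured receipt is p(1 − f) and the dilution is p × f. An illustrative p = 50% gives:

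| Assumed entry per year | f, 29 to 33 months | Measured receipt | Dilution (points) |
|---|---|---|---|
| 1% | 2.42–2.75% | 48.79–48.63% | 1.21–1.38 |
| 2% | 4.83–5.50% | 47.58–47.25% | 2.42–2.75 |
| 3% | 7.25–8.25% | 46.37–45.87% | 3.62–4.12 |
| 4% | 9.67–11.00% | 45.17–44.50% | 4.83–5.50 |
| 5% | 12.08–13.75% | 43.96–43.13% | 6.04–6.88 |

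At p = 80% the range is 1.9 to 11.0 points. The dilution equals the 4-point half-width when f = 4/50 = 8% (p = 50%) or f = 4/80 = 5% (p = 80%). At p = 50% this needs entry of roughly 3% per year.

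**Step 5. Precision after restriction (unweighted, P = 50%).**
- Removing only post-mailing entrants leaves 600 × (1 − 0.0242) = 585 down to 600 × (1 − 0.1375) = 517.5. The half-width 1.96 × √(0.25/n) is then 4.05 to 4.31 points.
- A cut at 3 completed years removes 36 months of entry, which is 3% to 15%. It leaves 582 to 510 and a half-width of 4.06 to 4.34 points.

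**Step 6. What the 3-year cut does.** The longest gap is 33 months, so anyone with 36 completed months of practice had started by the mailing. The cut also drops some who were already working then: up to 36 − 29 = 7 months of entry for the earliest French responses, and 36 − 33 = 3 months for the latest responses elsewhere.

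**The case against.** Much of the case on the other side stands.

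- **The limitation is disclosed.** Sections 9.5.1 and 9.9.5 both say that untargeted physicians may be included. A reader might infer that the protocol overlooked the issue. It did not. What remains is that the named remedy does not address it, and that 9.7.1 says something different.
- **A subgroup by duration of practice could sit in the SAP.** That is so, and its absence from the protocol is not the finding. The finding concerns what the protocol itself fixes: the definition of the targeted population and the screen.
- **Targeted is not used in one sense.** Sections 7.4 and 9.2.1 define it by specialty, and 9.7.2 uses it for physicians sent a survey invitation. None of these means individually mailed in 2014. This weakens any claim that the protocol formally labels late entrants as mailed. It does not take them out of the receipt denominator.
- **Surveying current prescribers is legitimate.** Whether today's prescribers know the restrictions is a proper question, and prescribers the letter never reached are a real gap. The all-respondent figure should therefore stay.
- **Reach.** A reader might infer that the whole effectiveness result is biased in every country and specialty. The documents do not support that. The per-question proportions of appropriate answers (9.7.1, 9.7.3) do not depend on receipt, and the EM went out from September 2015 to August 2016, when many later entrants could have received them.
- **Size.** A reader might also infer a bias as large as the planned precision. That depends on an outside entry rate. The protocol's 50% is a worst-case planning value for having received and understood the information, so it is not a DHPC-receipt rate.
- **Could not have received is too strong.** The Greek letter in Annex 4 asks recipients to share it with colleagues. Not in practice at the mailing is the safe wording.
- **The restricted subset is not those actually sent the letter.** The addressee line of the French letter does not name orthopaedists, yet Table 9.5.2–4 plans 50 of them among 180 French questionnaires. Restricting on duration of practice leaves them in.

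**Conclusion.** The point holds for DHPC receipt, and for the receipt component of the 9.7.1 objective as far as it rests on the DHPC. The frame admits physicians who began practice after the mailing, the prescribing screen cannot identify them, and they can only lower measured receipt.

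The size cannot be obtained from the documents. Under assumed entry of 1–5% per year and 50% receipt it is about 1 to 7 points, set against a planned half-width of 4. The calculation further assumes that later entrants prescribe and respond in proportion to their share, that none reports receipt, and that no weighting is applied. The knowledge items and EM awareness are outside the finding. It warrants a modest, inexpensive change to the reporting of one result; the sampling frame can stay as it is.

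**What to change.** 1. In 9.7.1, report DHPC receipt and the DHPC-dependent part of the objective in two lines: all respondents, as the estimate for current prescribers, and respondents already in practice at their country's DHPC date. Interpret the reach and effectiveness of the letter from the second line.
2. Derive the second group from duration of practice, for example 3 or more completed years. State that this cut is conservative. The questionnaire is a separate document not available here, so confirm that its response categories allow the cut and say whether the item means practice in the country and specialty.
3. Keep later entrants in the knowledge and EM results.
4. Reconcile the 9.7.1 statement that all physicians of the selected specialties were sent the DHPC and EM with the acknowledgements in 9.5.1 and 9.9.5, and say in 9.5.1 that the prescribing screen does not establish whether a physician was targeted.

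**Cost:** one derived variable and one table line. The half-width for that line is about 4.05 to 4.3 points instead of 4.0, unweighted. The subset still does not equal the physicians actually sent the letter, and the report should say so.

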**Table 9.5.1–1: Strata definition**

Stratum ID	Country	Specialty
1	France	GPs
2	France	Rheumatologists
3	France	Ortopedists / ortopedic surgeons
4	Greece	GPs
5	Greece	Rheumatologists
6	Greece	Ortopedists / ortopedic surgeons
7	Italy	GPs
8	Italy	Rheumatologists
9	Italy	Ortopedists / ortopedic surgeons
10	Portugal	GPs
11	Portugal	Rheumatologists
12	Portugal	Ortopedists / ortopedic surgeons

The physicians' allocation to a stratum is explained in the section below (§9.5.2. Study size calculation). However, eligible physicians are not evenly distributed across these four specialties. The GPs are much more prevalent..

### 9.5.2 Study size calculation

The sample size formula, based on the normal approximation to the binomial distribution, for calculating the number of subjects required for a proportion is the following:

$$n = \frac{P \cdot (1 - P) \cdot (Z_{1-\alpha/2})^2}{e^2}$$

Where  $P$  is the expected proportion,  $e$  is one half the desired width of the confidence interval (CI), and  $Z_{1-\alpha/2}$  is the standard normal  $Z$  value corresponding to a cumulative probability of  $1 - \alpha/2$ . The following table provides the margin of error for 95% CI based on various sample sizes and proportions of interest (Table 9.5.2–1).

**Table 9.5.2–1: Sample size obtained for various precisions and proportions**

Margin of error for 95% CI				
Proportion	5%	4%	3%	2%
10%	139	216	384	864

30%	323	504	896	2,017
50%	384	600	1,067	2,401
70%	323	504	896	2,017
90%	139	216	384	864

Since the proportion of physicians informed about the updated prescribing conditions and recommendations for safe use of systemic thiocolchicoside is not known and there is no evidence supporting the expected proportion, the worst case hypothesis will be assumed considering that 50% of physicians will have received and understood the safety information distributed recently. This assumption yields the largest sample size.

Considering this hypothesis and in order to achieve a CI of 95% with a half-width of 4%, a total of 600 analysable physician questionnaires will be needed for the overall sample. Considering a margin of error of 5% (or 3% respectively) instead of 4%, the required sample size would be 384 (or 1,067) analysable physician questionnaires for the overall sample.

Based on IMS Medical Radar experience from previous similar surveys and estimates and the evaluation of the survey feasibility with four countries, the sample size of 600 is considered for this study. Indeed, the elected sample size should be sufficient to be divided between 4 countries and further between 3 groups of specialities.

It is estimated that about 30% of physicians will not complete the questionnaire until the end or not be analysable (i.e. physicians who respond to questions regarding their knowledge on the updated safety concerns of systemic thiocolchicoside or physicians without any prescription of systemic thiocolchicoside in the last 12 months or physicians who have to interrupt the interview due to an emergency (rare)). Taking into account these respondent physicians without analysable questionnaires, the overall sample size of 780 participating physicians will be required to reach 600 analysable questionnaires (i.e. recruitment of physicians should continue until 600 analysable questionnaires have been reached).

For the conduct of survey, ideally this overall sample of 780 participating physicians (and 600 analysable questionnaires) should be proportionally split between the selected countries and specialties based on the number of physicians in each country. However, due to large variance of the number of physicians in targeted countries (Table 9.5.2–2) such a distribution would yield a too small number of interviews in smaller countries (such as Greece or Portugal) / specialties (such as rheumatologists) and would not allow the applicability of common statistical methods in those countries / specialties. For instance, an allocation of 600 analysable questionnaires using the true weight of each country (see column 'All % C') would yield the following sub-sample sizes per country: 353 physicians for France, 21 for Greece, 200 for Italy and 26 for Portugal.

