#### 4.8 Study size

The sample survey will include physicians from the IMS OneKey reference lists.

The sample size calculation is based on the survey objective, *i.e.* to measure the effectiveness of the DHPC and EM, on the awareness and understanding of prescribers of systemic thicolchicoside about the latest prescribing conditions and safety information/warnings of systemic thicolchicoside provided in the DHPC and EM.

Since the expected proportion of physicians who received and understood the latest prescribing conditions and safety information of systemic thicolchicoside is not known and there is no evidence supporting it, the worst case hypothesis will assume a proportion of 50%. For a confidence interval of 95% and a precision of 4%, a total of 600 analysable web-questionnaires will be needed for the overall sample: 180 in France and Italy, and 120 in Greece and Portugal.

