**Table 9.5.2–4: Sample size per country and per specialty**

n (vertical % per country)*	France	Greece	Italy	Portugal	All
Number of physicians with an analysable questionnaire	180	120	180	120	600
GPs	90 (50.0%)	60 (50%)	90 (50.0%)	60 (50%)	300 (50%)
Rheumatologists	40 (22.2%)	30 (25%)	40 (22.2%)	30 (25%)	140 (23.3%)
Orthopedists / orthopaedic surgeons	50 (27.8%)	30 (25%)	50 (27.8%)	30 (25%)	160 (26.7%)
Number of participating physicians required	234	156	234	156	780
GPs	117 (50%)	78 (50%)	117 (50%)	78 (50%)	390 (50%)
Rheumatologists	52 (22.2%)	39 (25%)	52 (22.2%)	39 (25%)	182 (23.3%)
Orthopedists / orthopaedic surgeons	65 (27.8%)	39 (25%)	65 (27.8%)	39 (25%)	208 (26.7%)

\* To be aligned with the n by country, numbers n per specialty have been rounded to the most closed integer.

Since the relative weight of each country and of each specialty in the sampling plan is different from its real relative weight in estimations, the extrapolation of the raw survey results to the overall target population would not be relevant.

A sample adjustment will be performed. The survey results will be weighted to reflect the real proportion of the four countries and within each country to reflect the real proportion of each specialty in order to extend the survey results to the overall target population. Both unweighted (i.e. raw data) and weighted results will be presented in the report.

A weight variable will be applied to each statistical unit (i.e. the analysable physician) during the results calculation in order to correct any over-or under-sampling that may have occurred for a country or specialty. This weight variable will indicate how many unit(s) of the population of interest an observation will count in a statistical procedure. Its value will change per country and per specialty. The weights will be normalised to obtain their sum equal to the sample size.

In order to fill-in each stratum of the sample survey from the IMS OneKey reference files, an independent sample will be selected per stratum through a simple random sampling without replacement.

In each specific stratum, physicians will be contacted according to the order of draw in this stratum. If a physician does not want to participate in the survey, the next one in order of

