draw will be contacted, and so on until the required number of physicians is met. If the target for a stratum is not achieved after the end of the initial list, an additional randomly sampled list will be prepared and the physicians contacted until the goal is reached or no names are left in that stratum. If the complete list of the IMS OneKey reference files has been exhausted in any particular stratum, a strategy will be determined to adjust the sample size within stratum with associated weighting.

In web surveys, the number of physicians to be contacted for reaching the required number of physicians with analysable questionnaires is usually around ten times more than the expected final number.

It is to be noted that this sample is calculated to be representative as a whole (including all countries), not per country or specialty. Thus the subgroup analyses will not guarantee the same confidence intervals as the whole sample. Indeed per country, a sub-sample of 180 analysable questionnaires for France and Italy will allow the estimation of the unknown expected proportion (supposed to be 50% for the sample size calculation) with a margin error of 7%. For Greece and Portugal, with 120 analysable questionnaires, the expected margin error will be around 9%.

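### The 4% overall half-width (7% and 9% by country) ignores the unequal allocation and the weighting; the weighted overall estimate has a half-width of about 6.4–6.5%

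*Protocol*

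**What the plan says.** Section 9.5.2 uses a formula "based on the normal approximation to the binomial distribution, for calculating the number of subjects required for a proportion", with no term for the sampling design. The planning value is the least favourable one: "the worst case hypothesis will be assumed considering that 50% of physicians will have received and understood the safety information distributed recently". From this the section concludes that "in order to achieve a CI of 95% with a half-width of 4%, a total of 600 analysable physician questionnaires will be needed". The abstract (section 4.8) says the same: "For a confidence interval of 95% and a precision of 4%, a total of 600 analysable web-questionnaires will be needed".

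The section then sets proportional allocation aside. Sharing 600 questionnaires by physician numbers would give "353 physicians for France, 21 for Greece, 200 for Italy and 26 for Portugal". The plan instead takes 180, 120, 180 and 120. Within each country, half the sample is GPs (Table 9.5.2–4), although Table 9.5.2–2 shows them as 60.2% to 94.5% of the listed physicians.

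Because of this, the text after Table 9.5.2–4 treats raw results as unsuitable for extrapolation and requires weighting by country and, inside a country, by specialty: "The survey results will be weighted to reflect the real proportion of the four countries and within each country to reflect the real proportion". Section 9.7.1 adds that the unweighted overall line does not reflect the countries' physician population, and section 9.9.5 repeats that raw results will not be generalised.

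For single countries, section 9.5.2 gives France and Italy, with 180 questionnaires each, a "margin error of 7%. For Greece and Portugal, with 120 analysable questionnaires, the expected margin error will be around 9" per cent.

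**The concern.** The precision is calculated for one estimator and the conclusions rest on another. The 4% belongs to the unweighted proportion, which describes an artificial mix of physicians that the protocol says must not be generalised. The estimate meant to represent the target population is the weighted one. Its variance depends on how the population shares line up with the stratum sample sizes, and here they line up badly.

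The country margins have the same fault. They use the raw country sample size, while the country results are also to be weighted by specialty (the weighted column of the mock table in section 9.7.1).

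The survey is descriptive and tests no hypothesis, so precision is the whole justification for its size. If the figures stand, a reader of the protocol, including the agency, will expect the generalisable result to be known to within 4 percentage points when the design gives about 6.5.

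**Working it through.** **1. The plan's own figures.** With P = 0.5, Z = 1.96 and e = 0.04, n = P(1−P)Z²/e² = 600.2. The half-width Z·√(0.25/n) is 4.0% for n = 600, 7.3% for n = 180 and 8.9% for n = 120. All the stated figures reproduce, but as unweighted simple random samples.

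**2. Inputs for the weighted estimate.** Population counts N_h are from Table 9.5.2–2 (total 163,178), stratum sample sizes n_h from Table 9.5.2–4, and W_h = N_h/163,178. Rheumatologist counts for Greece, Italy and Portugal are not available; they are first set to zero and then varied.

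**3. Formula.** For a stratified estimator, Var = Σ W_h²·P(1−P)/n_h. The design effect relative to 600 is 600·Σ(W_h²/n_h). The finite population correction is negligible in the strata that dominate.

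| Stratum | N_h | n_h | W_h | W_h²/n_h (×10⁻⁶) |
|---|---|---|---|---|
| France GP | 90,630 | 90 | 0.5554 | 3,427.5 |
| France rheumatologist | 2,353 | 40 | 0.0144 | 5.2 |
| France orthopedist | 2,936 | 50 | 0.0180 | 6.5 |
| Greece GP | 3,494 | 60 | 0.0214 | 7.6 |
| Greece orthopedist | 2,314 | 30 | 0.0142 | 6.7 |
| Italy GP | 45,203 | 90 | 0.2770 | 852.7 |
| Italy orthopedist | 9,234 | 50 | 0.0566 | 64.0 |
| Portugal GP | 5,943 | 60 | 0.0364 | 22.1 |
| Portugal orthopedist | 1,071 | 30 | 0.0066 | 1.4 |
| **Sum** | 163,178 | | | **4,393.8** |

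Design effect = 600 × 0.0043938 = 2.64. Effective n = 1/0.0043938 = 228. Half-width = 1.96·√(0.25 × 0.0043938) = 6.50%.

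**4. Missing rheumatologist counts.** The share in each of the three countries is an assumption; the French share is 2.5%.

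| Assumed share | Design effect | Effective n | Half-width |
|---|---|---|---|
| 0% | 2.64 | 228 | 6.50% |
| 1% | 2.61 | 229 | 6.47% |
| 2.5% | 2.58 | 232 | 6.43% |
| 5% | 2.53 | 237 | 6.36% |

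**5. Where the loss arises.** French GPs contribute 3,427.5/4,393.8 = 78% of the variance. With every other stratum known exactly, that stratum alone gives 1.96·√(0.25 × 0.0034275) = 5.7%. Weighting by country alone, with the shares in the table (58.8%, 3.6%, 33.4%, 4.3%), already gives 5.0%.

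**6. Countries.** The same formula is used with shares within each country. For France, Σ = 0.9449²/90 + 0.0245²/40 + 0.0306²/50 = 0.009953, so the design effect is 180 × 0.009953 = 1.79 and the half-width is 1.96·√(0.25 × 0.009953) = 9.8%.

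| Country | Stated | Weighted (share 0–5%) |
|---|---|---|
| France | 7% | 9.8% |
| Italy | 7% | 8.5–8.9% |
| Greece | about 9% | 9.9–10.4% |
| Portugal | about 9% | 10.5–11.1% |

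**7. Cost of a true 4%.** With the same allocation, the weighted estimate would need 600 × (6.36/4)² to 600 × (6.50/4)², about 1,520 to 1,580 questionnaires.

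**The case against.** The formula is applied correctly, the over- and under-sampling is disclosed openly, both weighted and unweighted results will be reported, and the protocol warns that subgroup intervals will be wider than the overall one. No test, threshold or decision rule depends on the 4%. The report will carry intervals calculated from the data, and the variance method for weighted proportions may be set in an analysis plan that is not at hand. It is therefore not shown that the reported intervals will be too narrow. That last point stands: the demonstrated error is in the planned precision.

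It is also true that the exact values are conditional. Final weights may come from the OneKey lists, whose counts are not in the protocol, and stratum sizes may shift if specialists cannot be recruited. If all rheumatologist places in Greece, Italy and Portugal went to GPs, with no weight for rheumatologists there, the country half-widths would be 9.5%, 7.5% and 9.2%, much closer to those stated. France would stay at 9.8% and the overall figure would still be 6.3%.

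A planning value of 50% is the worst case. At 10% or 90% the weighted half-width is 3.9%, but the unweighted one is then 2.4%, so the relative loss is the same.

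None of this restores the stated figures. The warning about subgroups leaves the overall 4% untouched, and its own 7% and 9% use raw counts.

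**Conclusion.** The concern holds. For the estimate the protocol intends to generalise, the planned 95% half-width is 6.4–6.5%, about 1.6 times the stated 4%, and the effective sample size is about 228–237 of 600. The country margins are also too small for weighted results, most clearly for France (9.8% against 7%). This rests on P = 50% in every stratum, weights from Table 9.5.2–2, the allocation in Table 9.5.2–4, and rheumatologist shares of 0–5% where the count is missing. Other weights would move the exact value. The direction is secure as long as French GPs hold a far larger share of the population than their 15% of the sample (90/600). The 4% remains correct only for the unweighted sample.

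**What to change.** Keep 600 and the allocation, and correct the precision statements in sections 4.8 and 9.5.2:

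- Give about 4% as the half-width of the unweighted sample and about 6.5% as that of the weighted overall estimate.
- Replace the 7% and 9% by weighted country half-widths of about 10% for France, 9% for Italy, 10% for Greece and 11% for Portugal.
- Next to Table 9.5.2–4, show the stratified variance formula and the design effect (about 2.5–2.6). State the conditions: P = 50%, weights from Table 9.5.2–2, and the assumed rheumatologist shares. Say that the figures will be updated once the final weights are fixed.

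This costs protocol wording and a less favourable stated precision; no extra physicians are needed. If 4% is truly required for the weighted overall result, wording is not enough: the sample would have to grow to roughly 1,520–1,580 at this allocation, or more of it would have to move to French and Italian GPs at the expense of the smaller strata.
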